9.1.3 Follow-up on adverse events

An AE should be followed until it has resolved, has a stable sequelae, the Investigator determines that it is no longer clinically significant, or the subject is lost to follow-up.

If an AE is still ongoing at the end of the study for a subject, follow-up should be provided until resolution/stable level of sequelae, the Investigator no longer deems that it is clinically significant, or until the subject is lost to follow-up. If no follow-up is provided, the Investigator must provide a justification. The follow-up will usually be continued for 30 days after the subject has discontinued their IMP.

Information on SAEs obtained after clinical database lock will be captured through the Patient Safety (PS) database without limitation of time.

9.1.4 Pregnancy

Should a subject become pregnant after the first intake of any IMP, UCB's PS department should be informed immediately. The subject should be withdrawn from the study as soon as the pregnancy is known and the following should be completed:

- The subject should return for an EDV.
- The subject should immediately stop the intake of the IMP or be down titrated as instructed at the EDV.
- A SV should be scheduled 2 weeks after the subject has discontinued their IMP.

The Investigator must inform the subject/parent(s)/legal representative(s) of information currently known about potential risks and about available treatment alternatives.

The Investigator will complete the Pregnancy Report and Outcome form for any pregnancy and send it to UCB's PS department (for contact details see SAE reporting information at the beginning of this protocol).

A pregnancy becomes an SAE in the following circumstances: miscarriage, abortion, or anomaly/birth defect of the child. Those SAEs must be additionally reported using the Investigator SAE Report form.

In cases where the partner of a male subject enrolled in a clinical study becomes pregnant, the Investigator or designee is asked to contact the subject to request consent of the partner via the Partner Pregnancy Consent form that has been approved by the responsible IRB/IEC and should be available in the Investigator site file. In case of questions about the consent process, the Investigator may contact the UCB/contract research organization contract monitor for the study.

If the partner has agreed that additional information can be captured and has provided the signed Partner Pregnancy Consent form, the Pregnancy Report and Outcome form will be completed. UCB's PS department is the primary contact for any questions related to the data collection for the partner pregnancy, eventual birth, and follow-up.

9.1.5 Suspected transmission of an infectious agent via a medicinal product

A suspected transmission of infectious agent is defined as any infection that is temporally related to the administration of the medicinal product with no other likely cause. The Medical Monitor should be contacted immediately. No further medicinal product from that specific batch should be administered. Infections should be treated according to normal clinical practice.

For the purposes of reporting, any suspected transmission of an infectious agent via a medicinal product should be considered as an SAE; such cases must be reported immediately, recorded in the AE module of the eCRF, and followed as any other SAE. Any organism, virus, or infectious particle (eg, prion protein transmitting transmissible spongiform encephalopathy), pathogenic or nonpathogenic, is considered an infectious agent.

9.1.6 Overdose of investigational medicinal product

Excessive dosing (beyond that prescribed in the protocol and including overdose) should be recorded on the eCRF. Any SAE or nonserious AE associated with excessive dosing must be followed as any other serious or nonserious AE. These events may be symptomatic, in that the excessive dosing results in clinical signs and symptoms, or the excessive intake may itself be a symptom.

9.1.7 Safety signal detection

Selected data from this study will be reviewed periodically to detect as early as possible any safety concern(s) related to the IMP so that Investigators, clinical study subjects, regulatory authorities, and IRBs/IECs will be informed appropriately and as early as possible.

The Study Physician or medically qualified designee/equivalent will conduct an ongoing review of SAEs and perform ongoing SAE reconciliations in collaboration with the Patient Safety representative.

As appropriate for the stage of development and accumulated experience with the IMP, medically qualified personnel at UCB may identify additional safety measures (examples: AEs, vital signs, laboratory, or ECG results) for which data will be periodically reviewed during the course of the study.

9.2 Laboratory measurements

9.2.1 Laboratory assessments for safety

Laboratory assessments for safety (including hematology, biochemistry, and endocrinology for all subjects, and urinalysis for subjects for whom sample collection is feasible) will be conducted using standard methods at a central laboratory. The central laboratory will provide the Investigator with dedicated, standardized sampling equipment (labels, needles, tubes) and a study-specific laboratory manual, which will explain how to use the equipment and how to ship the samples to the central laboratory.

For blood samplings, methods to minimize pain are recommended (eg, topical anesthetic and microsamplings will be used).

The total blood volume drawn for clinical laboratory assessments in subjects ≥ 2 years of age will be a maximum of 11mL per sampling, which includes up to 3mL for hematology and up to 8mL for biochemistry. For subjects < 2 years of age, the blood volume drawn will be typically much smaller and in the range of 1mL to 2.5mL. Further details will be provided in the laboratory manual.

This document cannot be used to support any marketing authorization application and any extensions or variations thereof.
PUBLIC COPY

The following laboratory parameters will be measured:

Hematology	Biochemistry	Urinalysis ^a	Pregnancy	Endocrinology
WBC	Glucose	Glucose	β -hCG ^d	FSH
RBC	Sodium	Ketones		LH
Hemoglobin	Potassium	Occult blood		TSH
Hematocrit	Calcium	Protein		T3
MCV	Chloride	Nitrites		T4
MCH	Bicarbonate	Leukocytes		
MCHC	Phosphorus (inorganic)	Microscopic examination ^c		
Platelet count	Total protein			
Lymphocytes (number, %)	Albumin			
Monocytes (number, %)	Total bilirubin ^b			
Neutrophils (number, %)	ALP ^b			
Eosinophils (number, %)	AST (SGOT) ^b			
Basophils (number, %)	ALT (SGPT) ^b			
	GGT ^b			
	Uric acid			
	Urea			
	Creatinine			
	Triglycerides			
	Cholesterol			

ALP=alkaline phosphatase; ALT=alanine aminotransferase; AST=aspartate aminotransferase;
 β -hCG=beta-human chorionic gonadotropin; FSH=follicle-stimulating hormone;
GGT=gamma-glutamyltransferase; LH=luteinizing hormone; MCH=mean corpuscular hemoglobin;
MCHC=mean corpuscular hemoglobin concentration; MCV=mean corpuscular volume; RBC=red blood cell;
ScrV=Screening Visit; SGOT=serum glutamic oxaloacetic transaminase; SGPT=serum glutamic pyruvic transaminase; T3=triiodothyronine; T4=tetraiodothyronine; TSH=thyroid-stimulating hormone;
TV=Titration Visit; WBC=white blood cell

^a Urinalysis will be performed for subjects for whom sample collection is feasible.

^b This assessment is used for hepatic monitoring.

^c Includes bacteria, cells, casts, and crystals for all samples.

^d Urine pregnancy tests should be conducted at the site for all female subjects of childbearing potential.

The creatinine clearance will be calculated over time by the central laboratory using their current methods. The subject's age, body weight and height, and gender must be recorded on the laboratory requisition form.

All female subjects of childbearing potential should have urine pregnancy tests. A serum pregnancy test will be performed as backup if a urine sample is not available. A urine pregnancy test should be performed at any time during the study if a pregnancy is suspected. All urine pregnancy tests should be conducted at the site.

Results for hematology, biochemistry, urinalysis, pregnancy tests, and endocrinology measurements will be provided by fax to the Investigator within 72 hours after sample receipt.

9.2.2 Evaluation of PDILI

The PDILI IMP discontinuation criteria for this study are provided in [Section 6.3.1](#), with the accompanying required follow-up investigation and monitoring detailed below. All PDILI events must be reported as an AE and reported to the study site and Sponsor within 24 hours of learning of their occurrence. Any PDILI event that meets the criterion for potential Hy's Law must be reported as an AE of special interest (see [Section 9.1.1.3](#)), and, if applicable, also reported as an SAE (see [Section 9.1.2.3](#)).

Evaluation of PDILI consists of the diagnostic testing and continued monitoring included in [Table 9–2](#) (specific tests dependent on laboratory results and corresponding symptoms) and consultation with a local hepatologist (if applicable; discussed in [Section 9.2.2.1](#)). The local hepatologist is the expert usually consulted by the treating physician for assessment and management of potential hepatic disease. This would usually be a hepatologist, but may be a gastroenterologist. Additional investigation and monitoring may be required and adapted based on the diagnosis after the cause of the liver injury/abnormality is confirmed (details in [Section 9.2.2.4](#)).

The results of all monitoring, including laboratory testing and other testing, should be made available to the study site and Sponsor.

All initial tests resulting in abnormal hepatic laboratory values need to be repeated, but appropriate medical action must not be delayed waiting for the repeat result.

If tests are done locally for more rapid results, a concurrent sample should also be sent to the central laboratory whenever possible. Medical care decisions are to be made initially using the most rapidly available results and a conservative approach must be taken if the results from the 2 laboratory tests are significantly different. Data from the local and central laboratory are to be recorded on the applicable eCRF pages.

When IMP is discontinued, all concomitant medications and herbal supplements that are not medically necessary should also be discontinued. In these cases, the Investigator should also consider dose reduction for medically necessary concomitant medication and consider changing any medically required concomitant medication known to be hepatotoxic to a suitable alternative.

Rechallenge with a substance potentially causing drug-induced liver injury is dangerous, may be fatal, and must not occur.

The table below summarizes the approach to investigate PDILI.

This document cannot be used to support any marketing authorization
application and any extensions or variations thereof.

PUBLIC COPY

Table 9–2: Required investigations and follow up for PDILI

Laboratory value		Symptoms ^a of hepatitis or hypersensitivity	Immediate		Follow up	
ALT or AST	Total bilirubin		Consultation requirements	Actions	Testing	Evaluation
≥3xULN	≥2xULN ^b	NA	Hepatology consult. ^c Medical Monitor must be notified within 24 hours (eg, by laboratory alert) and subject discussed with Medical Monitor ASAP.	Immediate, permanent IMP discontinuation.	Essential: Must have repeat liver chemistry values and additional testing completed ASAP (see Section 9.2.2.3); recommended to occur at the site with HCP.	Monitoring of liver chemistry values at least twice per week until values normalize, stabilize, or return to within baseline values. ^d
≥3xULN	NA	Yes		Immediate, temporary or permanent, IMP discontinuation.		
≥5xULN (and ≥2x baseline)	<2xULN	No	Discussion with Medical Monitor required. Hepatology consult required if ALT/AST ≥8x ULN.	Immediate, permanent IMP discontinuation.	Essential: Every attempt must be made to have repeat liver chemistry values and additional testing completed within 48 hours at the site with HCP (see Section 9.2.2.3).	

Table 9–2: Required investigations and follow up for PDILI

Laboratory value		Symptoms ^a of hepatitis or hypersensitivity	Immediate		Follow up	
ALT or AST	Total bilirubin		Consultation requirements	Actions	Testing	Evaluation
≥3xULN (and ≥2x baseline) and <5xULN	<2xULN	No	Discussion with Medical Monitor required if the criterion that allows for IMP continuation is met.	Further investigation – immediate IMP discontinuation not required (see Section 9.2.2.2). IMP discontinuation required if any of the following occur: 
• Subject cannot comply with monitoring schedule.• Liver chemistry values continue to increase• Liver chemistry values remain ≥3xULN (and ≥2x baseline) after 2 weeks of monitoring without stabilization or evidence of resolution.	Not required unless otherwise medically indicated (at discretion of Investigator).	Monitoring of liver chemistry values at least twice per week for 2 weeks. ^d Immediate IMP discontinuation required if: 
• Liver chemistry values continue to increase• Liver chemistry values remain ≥3xULN (and ≥2x baseline) after 2 weeks of monitoring without stabilization or evidence of resolution Continue to monitor until values normalize, stabilize, or return to within baseline values. ^d

Table 9–2: Required investigations and follow up for PDILI

Laboratory value		Symptoms ^a of hepatitis or hypersensitivity	Immediate		Follow up	
ALT or AST	Total bilirubin		Consultation requirements	Actions	Testing	Evaluation

ALP=alkaline phosphatase; ALT=alanine aminotransferase; ASAP=as soon as possible; AST=aspartate aminotransferase; HCP=healthcare practitioner; IMP=investigational medicinal product; NA=not applicable; PDILI=potential drug-induced liver injury; ULN=upper limit of normal

^a Hepatitis symptoms include fatigue, nausea, vomiting, and right upper quadrant pain or tenderness; hypersensitivity symptoms include eosinophilia (>5%), rash, and fever (without clear alternative cause).

^b If the subject also has $\geq 2 \times$ ULN ALP, the possibility of an indication of biliary obstruction should be discussed with the Medical Monitor.

^c Details provided in [Section 9.2.2.1](#). The local hepatologist is the expert usually consulted by the treating physician for assessment and management of potential hepatic disease. This would usually be a hepatologist, but may be a gastroenterologist.

^d Unless an alternative monitoring schedule is agreed by the Investigator and UCB responsible physician. Determination of stabilization is at the discretion of the Investigator in consultation with the hepatologist (as applicable) and UCB responsible physician, as needed.

9.2.2.1 Consultation with Medical Monitor and local hepatologist

Potential drug-induced liver injury events require notification of the Medical Monitor within 24 hours (eg, by laboratory alert), and the subject must be discussed with the Medical Monitor as soon as possible. If required, the subject must also be discussed with the local hepatologist. The local hepatologist is the expert usually consulted by the treating physician for assessment and management of potential hepatic disease. This would usually be a hepatologist, but may be a gastroenterologist. If determined necessary, this discussion should be followed by a full hepatology assessment (see [Section 9.2.2.3](#)) and SAE report (if applicable).

9.2.2.2 Immediate action: determination of IMP discontinuation

All PDILI events require immediate action, testing, and monitoring.

The immediate action is dependent on the laboratory values and symptoms of hepatitis or hypersensitivity and ranges from continuation of IMP (followed by immediate investigation) to immediate and permanent discontinuation (see [Section 6.3.1](#) and [Table 9–2](#) for details).

When IMP is discontinued, all concomitant medications and herbal supplements that are not medically necessary should also be discontinued. The Investigator should also consider dose reduction of medically necessary concomitant medication and consider changing any medically required concomitant medication known to be hepatotoxic to a suitable alternative.

9.2.2.3 Testing: identification/exclusion of alternative etiology

The measurements and additional information required for the assessment of PDILI events when there is a reasonable possibility that they may have been caused by the IMP are detailed in [Table 9–3](#) (laboratory measurements) and [Table 9–4](#) (additional information). Results of the laboratory measurements and information collected are to be submitted to the Sponsor on the corresponding eCRF. If the medical history of the subject indicates a requirement for other assessments not included below, these additional assessments should be completed and submitted, as applicable.

All blood samples should be stored, if possible. If tests are done locally for more rapid results, a concurrent sample must also be sent to the central laboratory.

The following measurements are to be assessed:

Table 9–3: PDILI laboratory measurements

Virology-related	Hepatitis A IgM antibody
	HBsAg
	Hepatitis E IgM antibody
	HBcAb-IgM
	Hepatitis C RNA
	Cytomegalovirus IgM antibody
	Epstein-Barr viral capsid antigen IgM antibody (if unavailable, obtain heterophile antibody or monospot testing)
Immunology	Anti-nuclear antibody (qualitative and quantitative)
	Anti-smooth muscle antibody (qualitative and quantitative)
	Type 1 anti-liver kidney microsomal antibodies (qualitative and quantitative)
Hematology	Eosinophil count
Urinalysis	Toxicology screen
Chemistry	Amylase
	If total bilirubin $\geq 2 \times$ ULN, obtain fractionated bilirubin to obtain % direct bilirubin
	Serum CPK and LDH to evaluate possible muscle injury causing transaminase elevation
Additional	Prothrombin time/INR ^a
	Serum pregnancy test ^b
	PK sample ^c

CPK=creatine phosphokinase; HBcAb-IgM=hepatitis B core antibody-IgM; HBsAg=hepatitis B surface antigen; IgM=immunoglobulin M; INR=international normalized ratio; LDH=lactate dehydrogenase; PDILI=potential drug-induced liver injury; PK=pharmacokinetic; RNA=ribonucleic acid; ULN=upper limit of normal

^a Measured only for subjects with ALT $>8 \times$ ULN, elevations in total bilirubin, and symptoms of hepatitis or hypersensitivity. Hepatitis symptoms include fatigue, nausea, vomiting, and right upper quadrant pain or tenderness; hypersensitivity symptoms include eosinophilia ($>5\%$), rash, and fever (without clear alternative cause).

^b Determined only for female subjects of childbearing potential.

^c Blood sample for determination of plasma concentrations of BRV.

The following additional information is to be collected:

Table 9–4: PDILI information to be collected

New or updated information
Concomitant prescription and over-the-counter medications (eg, acetaminophen, herbal remedies, vitamins); dosages and dates should be included.
Pertinent medical history, including the following: 
History of liver disease (eg, autoimmune hepatitis, nonalcoholic steatohepatitis or other “fatty liver disease”)Adverse reactions to drugsAllergiesRelevant family history or inheritable disorders (eg, Gilbert’s syndrome, alpha-1 antitrypsin deficiency)Recent travelProgression of malignancy involving the liver (Note: Metastatic disease to the liver, by itself, should not be used as an explanation for significant AST and/or ALT elevations.)
The appearance or worsening of clinical symptoms of hepatitis or hypersensitivity (eg, fatigue, nausea, vomiting, right upper quadrant pain or tenderness, decreased appetite, abdominal pain, jaundice, fever, or rash)
Recent clinically significant hypotension or hypoxemia with compromised cardiopulmonary function
Alcohol and illicit drug use, if applicable
Results of liver imaging or liver biopsy, if done
Results of any specialist or hepatology consult, if done
Any postmortem/pathology reports

ALT=alanine aminotransferase; AST=aspartate aminotransferase; PDILI=potential drug-induced liver injury

9.2.2.4 Follow-up evaluation

Potential drug-induced liver injury events will require follow-up monitoring as described in [Table 9–2](#). Monitoring should continue until liver chemistry values normalize, stabilize, or return to baseline. Determination of stabilization is at the discretion of the Investigator in consultation with the hepatologist (as applicable) and UCB responsible physician, as needed.

9.2.3 Plasma concentration measurements

9.2.3.1 BRV plasma concentrations

Blood samples for the analysis of BRV concentrations will be collected at the visits designated in [Table 5–2](#). Additionally, a blood sample for determination of BRV plasma concentration should be taken whenever the subject experiences an SAE.

Brivaracetam will be assayed in batch runs at the bioanalytical laboratory. Plasma levels will be reported to the central laboratory after the batch run is performed, according to laboratory

methodology. Results will be reported by the central laboratory to the Investigator as exact values, with a flag to those values that are outside the therapeutic range.

9.2.3.2 Phenytoin plasma concentrations (if applicable)

Subjects receiving phenytoin as a concomitant AED during the study will have blood samples collected at the visits designated in [Table 5–1](#), [Table 5–2](#), and [Table 5–3](#) to monitor phenytoin plasma concentrations.

Phenytoin plasma levels will be determined by the central laboratory. Further details on sample collection, bioanalytical method, and shipping of the samples will be provided in the central laboratory manual.

9.3 Other safety measurements

Other safety measurements will be performed at the visits indicated in [Table 5–1](#), [Table 5–2](#), and [Table 5–3](#).

9.3.1 ECG

A standard 12-lead ECG will be performed. The Investigator will determine whether the results of the ECG are normal or abnormal and assess the clinical significance of any abnormalities.

The original ECG tracing will be signed or initialed and dated by the Investigator, and retained as part of the source documentation.

9.3.2 Vital signs

Vital signs, including measurements of blood pressure, supine or sitting pulse rate, and body temperature, will be performed after 5 minutes of rest. Vital signs measurements will be repeated after 30 minutes if unusual values are observed at the initial reading.

9.3.3 Body weight, height, and head circumference

Body weight (subject wearing light clothing without shoes), height (length may be used for this measure, as appropriate), and head circumference (occipital-frontal circumference) will be measured.

9.3.4 Physical examination

A standard physical examination will be performed. Clinically significant new or worsened abnormalities discovered at the physical examination must be reported as AEs.

The Investigator or qualified designee will evaluate the subject's physical development using the 3-item Tanner scale. The Investigator should use clinical judgment in deciding which subjects are selected for evaluation of Tanner Stage (ie, those subjects who are pubescent at Baseline).

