4.3 Other variables

For subjects ≥ 2 years of age (based on DRC data):

- Responder rate (the percentage of subjects who have a $\geq 50\%$ reduction in seizure frequency per 28 days from Baseline for POS)
- Absolute change in seizure frequency (total seizures) per 28 days from Baseline to the end of the Evaluation Period
- Percent change in seizure frequency (total seizures) per 28 days from Baseline to the end of the Evaluation Period
- Seizure freedom over the Evaluation Period
- Proportion of seizure-free days over the Evaluation Period

For subjects < 2 years of age or subjects with absence seizures based on the DRC seizure counts:

- Seizure freedom rate over the Evaluation Period (all types) by visit and by time intervals (6 months, 12 months, etc.)
- Proportion of seizure-free days over the Evaluation Period (all types) and by time intervals (6 months, 12 months, etc.)
- Absolute worsening in ADF of total seizures (all types)
- Percent worsening in ADF of total seizures (all types)

- A descriptive summary of seizure frequency by visit based on the DRC data will be also provided for these subjects

In addition for subjects <2 years of age (based on EEG data [recorded at least 24 hours]) or subjects with absence seizures (based on EEG data):

- Responder rate for total POS defined as the percentage of subjects with a $\geq 50\%$ reduction in ADF of POS recorded on EEG
- Absolute change in ADF of total seizures (all types)
- Percent change in ADF of total seizures (all types)
- Seizure freedom (rate and proportion)
- Absolute worsening of other types of seizures
- Percent worsening of other types of seizures

For subjects with absence seizures:

- Number and type of nonabsence seizure

For all subjects:

- Physical (including Tanner staging, if applicable depending on subject's developmental status)
- Neurological examinations
- Psychiatric and mental status
- Laboratory tests (hematology, biochemistry including hepatic monitoring of ALT, AST, ALP, total bilirubin, and GGT, endocrinology [follicle-stimulating hormone, luteinizing hormone, thyroid-stimulating hormone, triiodothyronine, and tetraiodothyronine] for all subjects and urinalysis for subjects for whom sample collection is feasible) (See Section 9.2.1)
- ECG
- Vital signs (blood pressure, pulse rate, and body temperature)
- Body weight
- Height and head circumference
- Plasma concentrations of BRV and phenytoin (if applicable)

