5.1.1 Study duration per subject

Subject participation will extend from study entry for at least 3 years until approval of BRV has been obtained for pediatric subjects in their age range, until a managed access program is established as allowed per country-specific requirements in addition to legal and regulatory guidelines, until subjects transition to another BRV study, or until the investigational product development in the related age range of the pediatric population is stopped by the Sponsor, whichever comes first.

Study entry is defined as the EV for LTFU subjects and the ScrV for directly enrolled subjects.

The end of the study is defined as the date of the last visit of the last subject in the study.

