- For subjects \geq 2 years of age at V5 who have typical absence seizures, an EEG of at least 1 hour that includes hyperventilation and intermittent photic stimulation must be performed at V5 and yearly thereafter. For subjects prematurely discontinuing from the study, an at least 1-hour EEG may be performed at the EDV at the Investigator's discretion.
- For subjects <2 years of age at V5, an EEG of at least 24 hours must be performed for efficacy assessment at V5 and yearly thereafter until subjects reach 2 years of age. For subjects prematurely discontinuing from the study, an at least 24-hour EEG may be performed at the EDV at the Investigator's discretion.

^g No DRC or study drug will typically be dispensed at the FV. However, for subjects who complete the study but do not continue BRV treatment, study drug for down-titration will be dispensed.

^h The assessment of seizure types will be done at 6-monthly intervals (at the FEV and the YEV) for subjects <2 years of age.

ⁱ For subjects enrolled in N01266 who volunteered to participate in EP0065 and then returned to N01266, changes to ongoing concomitant medications during EP0065 will be recorded in the N01266 eCRF.

^j For subjects enrolled in N01266 who volunteered to participate in EP0065 and then returned to N01266, ongoing AEs that stop during EP0065 will be recorded in the N01266 eCRF.

^k Drug return includes study medication intake recording and accountability.

^l Full laboratory assessments for safety include hematology, biochemistry (including hepatic monitoring of ALT, AST, ALP, total bilirubin, and GGT), and

Table 5–2: Schedule of all study assessments for the Evaluation, Down-Titration, and Safety (Drug-Free) Periods (all subjects)

Period	Evaluation						Down-Titration	Safety (Drug-Free)
	Minimal Evaluation Visit (MEV)	Full Evaluation Visit (FEV)	Yearly Evaluation Visit/Final Visit (YEV/FV ^a)	Unscheduled Visit (UV)	Early Discontinuation Visit (EDV)	Down-Titration Visit (DTV) ^b		
Assessment								

endocrinology for all subjects and urinalysis for subjects for whom sample collection is feasible as described in Section 9.2.1. Female subjects of childbearing potential should have a urine pregnancy test done at the site at all laboratory assessment visits. Endocrinology testing will be performed at the YEV/FV.

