8.1 Screening Visit for directly enrolled subjects only

The ScrV is applicable only to directly enrolled subjects (ie, subjects ≥ 4 years to <17 years of age with POS who have not participated in a core study). The Screening Period will serve as the Baseline Period for directly enrolled subjects. The ScrV is not applicable for LTFU subjects; the first N01266 visit for LTFU subjects is the Entry Visit (Section 8.3.1).

The ScrV assessments will be conducted 7 ± 2 days prior to the first administration of BRV. It is acceptable for the ScrV assessments to be conducted on more than 1 day.

The ScrV assessments are as follows:

- Signing and dating of written Informed Consent by parent(s)/legal representative(s)
- Signing and dating of Assent form by the subject (if applicable, according to age and local requirements)
- Subject identification card dispensing
- Demographic data
- Childbearing potential

- Verification of inclusion/exclusion criteria
- Physical (including Tanner Scale, as applicable) and neurological examinations
- Psychiatric and mental status
- General medical and procedures history
- Epilepsy and AED history
- Vital signs (blood pressure, pulse rate, and body temperature)
- Body weight, height, and head circumference
- ECG
- EEG (A previous EEG documenting the POS diagnosis must be available at the ScrV for directly enrolled subjects. If an EEG is not available at the ScrV, it must be scheduled during the Screening Period.)
- Neuro-imaging procedure (brain magnetic resonance imaging/brain computerized tomography scan [except in Germany]/ultrasounds or any other imaging test) should be performed if no report is available within the previous 2 years
- DRC dispensed
- Recording of medications
- Recording of procedures
- Recording of AEs
- IVRS call
- Laboratory assessments for safety including:
 - Hematology
 - Biochemistry including hepatic monitoring
 - Urinalysis (for subjects for whom sample collection is feasible)
 - Endocrinology
 - Urine pregnancy test (see Section 9.2.1)
- Phenytoin plasma concentrations (if applicable)
- Suicidality assessment (C-SSRS-Baseline/Screening) (for subjects ≥ 6 years of age)
- Achenbach CBCL (version consistent with age at the visit)
- BRIEF-P (<5 years of age)/BRIEF (≥ 5 years of age) (version consistent with age at the visit)
- PedsQL (version consistent with age at the visit)
- Appointment for the next visit (TV1) 7 ± 2 days later

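### Section 9.3.4 fixes Tanner staging eligibility at Baseline while Section 4.3 ties it to developmental status, so puberty that begins on BRV may go unstaged or be staged inconsistently

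*Protocol*

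**What the plan says.** Protocol Section 9.3.4 (Physical examination) says that physical development is evaluated on the 3-item Tanner scale. It then states: "The Investigator should use clinical judgment in deciding which subjects are selected for evaluation of Tanner Stage". A parenthesis introduced by *ie* defines the group as those "selected for evaluation of Tanner Stage (ie, those subjects who are pubescent at Baseline".

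Section 4.3 (Other variables), under the heading for all subjects, lists: "Physical (including Tanner staging, if applicable depending on subject's developmental status". It sets no Baseline condition.

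Among the visit lists in Section 8, only the Screening Visit for directly enrolled subjects mentions the scale (Section 8.1): "Physical (including Tanner Scale, as applicable) and neurological examinations". The lists for the Entry Visit of directly enrolled subjects (8.3.2) and for the Full Evaluation (8.5), Yearly Evaluation (8.6), Early Discontinuation (8.8), Safety (8.10) and Final (8.11) Visits give a physical examination without mentioning Tanner staging.

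FSH and LH belong to the endocrinology panel. A footnote to Table 5-2 says: "Endocrinology testing will be performed at the YEV/FV". On duration, Section 5.1.1 says: "Subject participation will extend from study entry for at least 3 years until approval of BRV" and then names further stopping conditions, "whichever comes first".

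**The concern.** Being pubescent at Baseline is settled once per child. Developmental status changes with age. In a long-term paediatric study the two tests separate for one group: children who are prepubertal at Baseline and reach puberty while taking BRV. They are the only subjects in whom the onset of puberty on treatment could be staged, since a child already pubescent at Baseline can show progression only. Section 9.3.4 leaves them out.

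Documenting long-term safety is the primary objective, and Section 5.4 says that the data will support applications for paediatric indications. Where 9.3.4 is followed, the FSH and LH results of these children have no clinical stage beside them. A stage that was not recorded at the visit cannot be recovered at analysis, so the SAP cannot repair the gap. Where some sites follow 4.3 and others 9.3.4, the stages that exist would come from an uneven selection of children.

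**Working it through.** The plan gives no figure on this point, so there is none to reproduce. The check is a comparison of sections, followed by an illustration on assumed numbers.

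**Who is selected**

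| Subject | Section 9.3.4 | Section 4.3 |
|---|---|---|
| Pubescent at Baseline | selected | applicable |
| Prepubertal at Baseline, enters puberty on study | not selected | applicable once developmental status warrants it |
| Prepubertal throughout | not selected | applicability depends on developmental status |

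The sections plainly diverge in the second row.

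**Whether such children can be in the study.** Section 2.3 admits long-term follow-up subjects from 1 month of age, and Section 6.1.3 admits directly enrolled subjects from 4 to under 17 years. Participation is planned for at least 3 years or until an earlier stopping condition. Prepubertal entrants who reach puberty on study are therefore to be expected.

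**Whether another section corrects 9.3.4.** Tanner is named at the Screening Visit, which only directly enrolled subjects attend and which precedes the first dose. No later visit list tells a site to begin staging a child who has reached puberty since then.

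**What Baseline means.** Section 8.1 makes the Screening Period the Baseline Period for directly enrolled subjects. For follow-up subjects, Section 12.5 takes Baseline from the core study, but says so for the rating scales. If the same meaning applies in 9.3.4, eligibility for these children is fixed before they enter this study and the excluded window is longer.

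**Illustration only.** None of these inputs is in the documents: entry ages uniform over 4 to under 17 years (a span of 13 years), complete follow-up of *f* years, and pubertal onset at a single age *a* between 9 and 12 years.

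- Share crossing onset on study = *f*/13. With *f* = 3: 3/13 = 23%.
- Share of all subjects pubertal at any time on study = *f*/(*f* + 17 − *a*). With *f* = 3 and *a* = 9: 3/11 = 27%. With *a* = 12: 3/8 = 38%.
- With a shorter assumed follow-up, *f* = 1: 1/13 = 8%, and 1/9 = 11% to 1/6 = 17%.

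Earlier stops and dropout lower these shares, as the last line shows. Follow-up subjects who enter below 4 years are left out of the denominator. The figures show only that the group need not be small.

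**The case against.** The strongest reply is that this is a mismatch of wording and that two tempting inferences go too far.

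A reader might infer that these children are never staged. The documents do not support that. Section 9.3.4 invokes clinical judgment, and Section 4.3 lists staging for all subjects without a Baseline limit. An investigator who relies on 4.3 may stage a child who becomes pubertal on study. This objection stands. What remains is that *ie* defines rather than illustrates, so as written the judgment operates inside a group fixed at Baseline, and 9.3.4 is the section that describes how the examination is done.

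A reader might also infer that pubertal onset cannot be assessed, or that an effect on its timing would go unseen. That is too strong as well. FSH and LH are sampled at the Yearly Evaluation and Final Visits, and at screening in directly enrolled subjects. Height and childbearing potential are recorded at the Minimal, Full and Yearly Evaluation Visits, the Final Visit and the Early Discontinuation Visit. Section 9.3.4 requires clinically significant new or worsened findings to be reported as adverse events, and treatment-emergent adverse events are a primary variable. None of these is a pubertal stage, so the information is indirect, but it exists.

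Two further points stand. No objective names puberty, and Tanner staging is an optional element of an 'other' variable. The study is single-arm and descriptive, so added stages could not by themselves attribute altered timing to BRV. These points limit the importance of the defect. They do not reconcile the two sections.

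**Conclusion.** The contradiction is real and is in the current text. Section 9.3.4 selects for staging by status at Baseline, and Section 4.3 by developmental status without that limit. Followed as written, 9.3.4 leaves children whose puberty begins on BRV without a Tanner stage. Followed unevenly alongside 4.3, it gives staging that differs between sites.

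The conclusion rests on reading *ie* as a definition and on the absence of any later visit list that names the scale. It does not depend on the percentages above, which rest on assumed ages and complete follow-up and should not be cited as estimates. The consequence is less complete safety data on one aspect of development. The primary analysis is unaffected. The change is worth making because it is cheap and missed stages cannot be recovered later.

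**What to change.** In Section 9.3.4, replace the Baseline condition with selection by the subject's developmental status at each scheduled physical examination, so that it agrees with Section 4.3. Name Tanner staging, as applicable, beside the physical examination in the Yearly Evaluation, Final and Early Discontinuation Visit lists (8.6, 8.11, 8.8). At the first two of these, FSH and LH are already sampled, so stage and hormone values would be recorded at the same visit. The Early Discontinuation Visit list has no endocrinology, so a stage there would stand alone.

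The cost is one sentence in 9.3.4, an addition to three visit lists, and matching eCRF guidance. No visit or blood sample is added. The downside is a slightly longer and more intimate examination in some older children. Recording stage 1 routinely in children judged prepubertal would give onset a starting point, but it is new data collection that the contradiction does not require, and it is not part of this recommendation.
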